3.1.1 Primary endpoints

The primary endpoints are safety and tolerability evaluations, assessed according to the Common Terminology Criteria (CTCAE), version 4.03. This includes the incidence of adverse events (AEs) by grade, incidence of serious adverse events (SAEs), changes from baseline in vital signs, as well as changes from baseline in laboratory results (hematology, blood chemistry, lipid profile, viral markers) qualifying as AEs.

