8.1 Adverse events

8.1.1 Definitions and reporting

An adverse event is defined as the appearance of (or worsening of any pre-existing) undesirable sign(s), symptom(s), or medical condition(s), that occur after patient's signed informed consent has been obtained.

Abnormal laboratory values or test results occurring after informed consent constitute adverse events only if they induce clinical signs or symptoms, are considered clinically significant, require therapy (e.g. hematologic abnormality that requires transfusion or hematological stem cell support), or require changes in study drug(s).

Except for screening failures, Adverse events that begin or worsen after informed consent should be recorded in the Adverse Events CRF. Conditions that were already present at the time of informed consent should be recorded in the Medical History/Current Medical Conditions CRF. Adverse event monitoring should be continued for at least 30 days (\pm 2 days) following the last dose of everolimus. Adverse events (including laboratory abnormalities that constitute AEs) should be described using a diagnosis whenever possible, rather than individual underlying signs and symptoms. When a clear diagnosis cannot be identified, each sign or symptom should be reported as a separate Adverse Event.

Adverse events will be assessed according to the Common Terminology Criteria for Adverse Events (CTCAE) version 4.03. If CTCAE grading does not exist for an adverse event, the severity of mild, moderate, severe, and life-threatening, corresponding to Grades 1 - 4, will be used. CTCAE Grade 5 (death) will not be used in this study; rather, information about deaths will be collected through a Death form.

The occurrence of adverse events should be sought by non-directive questioning of the patient (subject) during the screening process after signing informed consent and at each visit during the study. Adverse events also may be detected when they are volunteered by the patient during the screening process or between visits, or through physical examination, laboratory test, or other assessments.

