Progression of malignancy (including fatal outcomes), if documented by use of RECIST (version 1.1) will not be reported as a serious adverse event. Adverse events separate from the progression of malignancy (example, deep vein thrombosis at the time of progression or hemoptysis concurrent with finding of disease progression) will be reported as per usual guidelines used for such events with proper attribution regarding relatedness to the study drugs.

As far as possible, each adverse event should be evaluated to determine:

1. The severity grade (CTCAE Grade 1-4)
2. Its duration (Start and end dates or Ongoing at End of Study)
3. Its relationship to the study treatment (Reasonable possibility that AE is related: No, Yes)
4. Action taken with respect to study or investigational treatment (none, dose adjusted, temporarily interrupted, permanently discontinued, unknown, not applicable)
5. Whether medication or therapy was given (no concomitant medication/non-drug therapy, concomitant medication/non-drug therapy)
6. Whether it is serious, where a serious adverse event (SAE) is defined as in [Section 8.2.1](#)

All adverse events should be treated appropriately. If a concomitant medication or non-drug therapy is given, this action should be recorded on the Adverse Event CRF.

Once an adverse event is detected, it should be followed until its resolution or until it is judged to be permanent, and assessment should be made at each visit (or more frequently, if necessary) of any changes in severity, the suspected relationship to the study treatment, the interventions required to treat it, and the outcome.

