10.5 Primary objective

The primary objective is to evaluate the safety and tolerability profile of everolimus in post-menopausal women with ER positive, HER2 negative locally advanced or metastatic breast cancer after documented recurrence or progression following a non-steroidal aromatase inhibitor therapy in emergent growth markets (EGM).

The assessment of safety and tolerability will be based mainly on the frequency of adverse events, including the laboratory values that qualify as adverse events. Other safety data (e.g. vital signs, and special tests) will be considered as appropriate. The analysis will be descriptive. For all safety/tolerability analyses, the safety set will be used.

Data collected by AE CRFs will be coded using the MedDRA dictionary. The incidence of treatment-emergent adverse events (new or worsening from baseline) will be summarized by MedDRA system organ class and preferred term using frequency distributions. Additionally, AE will be summarized by maximum severity (based on CTCAE grades), and for AE with suspected drug relation, serious AE (SAE), and AE leading to permanent discontinuation of study drug. All information pertaining to AE noted during the study will be listed by patient, detailing the verbatim term given by the investigator, MedDRA preferred term and system organ class, start/end dates, severity, seriousness, relationship to study drug and action taken.

[figure not shown]
The AE onset will also be shown relative (in number of days) to the date of initial dose. AE starting more than 30 days after discontinuation of study drug will not be considered as treatment-emergent and will not be included in AE summary tables but listed only.

Data from other tests (e.g., electrocardiogram or vital signs) will be summarized descriptively as appropriate. Notable values will be flagged, and any other information collected will be listed as appropriate.

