Changes in patient's condition (investigator's discretion)	xx (xx.x)	NA	xx (xx.x)	NA	xx (xx.x)	NA

	Asian (N=xx)		Non-Asian (N=xx)		Total (N=xxx)	
	Everolimus (N=xxx)	Exemestane (N=xxx)	Everolimus (N=xxx)	Exemestane (N=xxx)	Everolimus (N=xxx)	Exemestane (N=xxx)
Need for other types of anticancer therapy (excluding palliative radiation for bone lesions)	xx (xx.x)	NA	xx (xx.x)	NA	xx (xx.x)	NA
Everolimus dose interruption > 4 wks	xx (xx.x)	NA	xx (xx.x)	NA	xx (xx.x)	NA
Other	xx (xx.x)	NA	xx (xx.x)	NA	xx (xx.x)	NA

NA: Not applicable SD: Standard deviation.

Asian: Indonesia, India, Vietnam, Turkey, South Korea, Thailand, Malaysia, Taiwan or Jordan.

Non-Asian: Australia, Morocco, South Africa or Tunisia.

^a Days with a zero dose level due are to temporary interruptions caused by safety reasons or patients' non-compliance.

^b Study treatment discontinuation refers to a patient's withdrawal from everolimus.

Table 6.1 Summary Overview of All Treatment-Emergent Adverse Events Summary, Any CTCAE Grade Overall and in Asian Subgroup - Safety Set

Adverse Event	Asian (N=xx)	Non-Asian (N=xx)	Total (N=xxx)
Number of patients, n (%)			
With no TEAE	xx (xx.x)	xx (xx.x)	xx (xx.x)
With at least one TEAE	xx (xx.x)	xx (xx.x)	xx (xx.x)
With at least one drug-related TEAE ^a	xx (xx.x)	xx (xx.x)	xx (xx.x)
With at least one serious TEAE	xx (xx.x)	xx (xx.x)	xx (xx.x)
TEAE leading to death	xx (xx.x)	xx (xx.x)	xx (xx.x)
Non-fatal serious TEAE	xx (xx.x)	xx (xx.x)	xx (xx.x)
With at least one serious drug-related TEAE, n (%)	xx (xx.x)	xx (xx.x)	xx (xx.x)
AE leading to death	xx (xx.x)	xx (xx.x)	xx (xx.x)
Non-fatal serious TEAE	xx (xx.x)	xx (xx.x)	xx (xx.x)
TEAE leading to treatment discontinuation, n (%)	xx (xx.x)	xx (xx.x)	xx (xx.x)
With at least one treatment-emergent AESI, n (%)	xx (xx.x)	xx (xx.x)	xx (xx.x)

Asian: Indonesia, India, Vietnam, Turkey, South Korea, Thailand, Malaysia, Taiwan or Jordan.

Non-Asian: Australia, Morocco, South Africa or Tunisia.

TEAE: Treatment emergent adverse event. TEAE are defined as any adverse event with a start date on or after the date of the first dose of study drug and within 30 days of treatment discontinuation. AESI = Adverse events of special interest.

Adverse events are coded using MedDRA version 19.1. AEs are assessed using CTCAE version 4.03.

Percentages are based on the number of patients in the Safety Set.

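### The SAP defines treatment-emergent AEs by start date alone and omits the worsening limb that protocol 10.5 uses for the primary-objective analysis

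*SAP*

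**What the plan says.** Protocol 10.5, on the analysis of the primary objective, states: "The incidence of treatment-emergent adverse events (new or worsening from baseline) will be summarized by MedDRA system organ class and preferred term". The statistical methods in the protocol summary use the same rule. Both exclude from the summary tables any AE that starts more than 30 days after study drug is stopped. Section 10.5 also undertakes to list all AEs noted during the study by patient.

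The SAP (section 1.2, footnote to Table 6.1, repeated under the later AE shells through Table 6.14.1) states: "TEAE are defined as any adverse event with a start date on or after the date of the first dose of study drug", with the same 30-day upper limit. Worsening is not mentioned. Nothing in the SAP as supplied restores it or explains its omission. Listings 14.1 to 14.3 are all titled as treatment-emergent.

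On recording, protocol 8.1.1 says: "An adverse event is defined as the appearance of (or worsening of any pre-existing) undesirable sign(s), symptom(s), or medical condition(s". It continues: "Adverse events that begin or worsen after informed consent should be recorded in the Adverse Events CRF", and "Conditions that were already present at the time of informed consent should be recorded in the Medical History/Current Medical Conditions CRF".

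**The concern.** AE incidence by grade is a primary endpoint and the study is descriptive, so these counts are the main result. Two definitions of treatment-emergent cannot both be programmed. The SAP's version can only give the same count as the protocol's or a lower one, so any discrepancy makes the combination look safer. The definition governs the tables by grade, relationship, seriousness, discontinuation, fatal outcome and special interest. An event lost from one can be lost from all of them, and from the listings too.

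**Working it through.** The documents give no planned AE rate or precision target, so there is no figure to reproduce. The check is to take each way an event can worsen and ask whether each rule counts it.

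1. **Event begins after first dose.** Counted under both rules.
2. **Condition present at consent, worse on treatment.** Section 8.1.1 sends the condition to medical history and makes its worsening an AE in its own right. That AE would normally carry an on-treatment start date. Counted under both.
3. **Significant laboratory or examination finding before dosing, worse on treatment.** Protocol 7.2.1 and 7.2.3 send the pre-dose finding to medical history, so this normally behaves as case 2. A residual route remains, because 8.1.1 also lets an abnormal value after consent qualify as an AE.
4. **AE begins between consent and first dose, and its grade increase on treatment is recorded with its own date.** Counted under both.
5. **As case 4, but the original start date is kept.** Counted under protocol 10.5, not under the SAP.
6. **AE begins before first dose and does not worsen.** Counted under neither.

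The rules differ only in case 5. Such records can exist: Table 7-1 collects AEs at screening, Day -21 to Day -1, and 8.1.1 opens the AE form from consent. Whether case 5 or case 4 applies depends on how a grade increase is recorded. Section 8.1.1 says "assessment should be made at each visit (or more frequently, if necessary) of any changes in severity", but not whether a change opens a new record or what start date it takes.

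**Scale, for illustration only.** The documents do not give the share of toxicity that falls in case 5. Take an 8% grade 3-4 rate. Protocol Table 1-1 gives this for anemia (7% + 1%) and for stomatitis (8% + 0%) on the combination in the earlier phase III trial. With the planned maximum of 400 patients, 0.08 × 400 = 32. For an assumed lost share f, the table would show 32 × (1 − f), rounded, over 400 (exact 95% intervals):

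- f = 0: 32, 8.0% (5.5 to 11.1)
- f = 5%: 30.4, rounded to 30, 7.5% (5.1 to 10.5)
- f = 10%: 28.8, rounded to 29, 7.25% (4.9 to 10.2)
- f = 20%: 25.6, rounded to 26, 6.5% (4.3 to 9.4)

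Every f above zero is an assumption. If each grade increase has its own dated record, f = 0.

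**The case against.** The strongest reply is that the SAP's rule may lose nothing. The protocol treats worsening of a pre-existing condition as a new AE, so most on-treatment worsening already has an on-treatment start date. The SAP also hints at grade-level records: the footnote to Table 6.2.1 counts a patient under every grade that one AE reached, and Listing 14.1 shows one grade, one start date and one end date per row. If each grade has its own row and date, the two definitions give the same counts. In any case, no hypothesis test or AE threshold depends on the result.

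Much of this stands. A reader might infer that the SAP discards every event that worsens on treatment; the recording rules in 8.1.1 rule that out. A reader might single out anemia, hyperglycemia or raised transaminases present before dosing as the main casualties; these are weak examples, because significant pre-dose laboratory findings go to medical history. A reader might also say that the SAP contradicts the endpoint definition. Section 3.1.1 says only "This includes the incidence of adverse events (AEs) by grade, incidence of serious adverse events (SAEs", without using the term treatment-emergent; the conflict is with the analysis text in 10.5 and the summary.

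Two parts do not stand. Row layout suggests grade-level dating but does not establish it. The CTC-grade shift tables (SAP Tables 10.2.2 and 10.3.2) are not a dependable backstop either. They cover laboratory values only, and protocol 7.1 and 7.2.3 keep those values in source documents, outside the CRF.

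**Conclusion.** The SAP departs from the protocol on the rule for the primary-objective AE tables, and the SAP text should be corrected. The consequence is narrow. It affects only AEs first recorded between consent and first dose that rise in grade on treatment, and only if the rise keeps the original start date. The documents leave that condition open.

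The size cannot be computed and may be zero; only the direction is known, towards fewer TEAEs. It would be tempting to conclude that toxicity is undercounted, or to put a percentage on the loss. The documents support neither, since they do not give the frequency of AEs arising in screening or the share that worsen. In the illustration, even an assumed 20% loss moves the estimate by 8.0 − 6.5 = 1.5 percentage points, inside the original interval.

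**What to change.** Replace the TEAE footnote throughout the SAP with: *an AE that starts, or increases in CTCAE grade from its pre-dose level, on or after the first dose of study drug and within 30 days after study drug discontinuation; a worsened event is counted at the worsened grade.*

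The definition needs data to support it. State in the CRF completion rules that each grade increase is recorded with its own date. If an event is held as one row with one grade and one start date, a program cannot tell when the grade rose. Where that has happened, sites need be queried only about AEs that began between consent and first dose and continued into treatment.

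Replace the TEAE-only Listing 14.1 with a listing of all AEs carrying a TEAE flag, as 10.5 promises. That would also show events starting more than 30 days after discontinuation, which 10.5 says are listed only.

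The cost is one changed definition, a derived flag, a revised listing and some data-recording work. If grade increases are already dated separately, only the SAP text and programming change. Neither patient procedures nor sample size is affected.

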10.6.1.1 Overall response rate

The Overall response rate (ORR) will be provided over the study period. The ORR is the proportion of patients with a best overall response of confirmed complete (CR) or partial (PR) response at those time points. The best overall response for each patient is determined from the sequence of investigator overall lesion responses according to RECIST 1.1. To be assigned a best overall response of CR at least two determinations of CR at least 4 weeks apart before progression are required. To be assigned a best overall response of PR at least two determinations of PR or better at least 4 weeks apart before progression (and not qualifying for a CR) are required.

The ORR (best overall response of CR or PR) as well as individual response categories (CR, PR, SD, PD or unknown) measured at approximately week 20 and week 50 will be summarized using frequency tables together with their associated two-sided exact 95% confidence intervals (Clopper-Pearson method).

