14.1.16 Best overall response

The best overall response is the best response recorded from the start of the treatment until disease progression/recurrence (taking as reference for PD the smallest measurements recorded since the treatment started). In general, the patient's best response assignment will depend on the achievement of both measurement and confirmation criteria.

The best overall response will usually be determined from response assessments undertaken while on treatment. However, if any assessments occur after treatment withdrawal the protocol should specifically describe if these will be included in the determination of best overall response and/or whether these additional assessments will be required for sensitivity or supportive analyses. As a default, any assessments taken more than 30 days after the last dose of study treatment will not be included in the best overall response derivation. If any alternative cancer therapy is taken while on study any subsequent assessments would ordinarily be excluded from the best overall response determination. If response assessments taken after withdrawal from study treatment and/or alternative therapy are to be included in the main endpoint determination, then this should be described and justified in the protocol.

Where a study requires confirmation of response (PR or CR), changes in tumor measurements must be confirmed by repeat assessments that should be performed not less than 4 weeks after the criteria for response are first met.

Longer intervals may also be appropriate. However, this must be clearly stated in the protocol.

The main goal of confirmation of objective response is to avoid overestimating the response rate observed. In cases where confirmation of response is not feasible, it should be made clear when reporting the outcome of such studies that the responses are not confirmed.

- For non-randomized trials where response is the primary endpoint, confirmation is needed.
- For trials intended to support accelerated approval, confirmation is needed
- For all other trials, confirmation of response may be considered optional.
- The best overall response for each patient is determined from the sequence of overall (lesion) responses according to the following rules:
- CR = at least two determinations of CR at least 4 weeks apart before progression where confirmation required or one determination of CR prior to progression where confirmation not required

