^a Best overall response rate: The best response recorded from baseline assessment until progression. CR: at least two consecutive determinations of CR at least 4 weeks or one determination of CR where confirmation not required prior to PD. PR: at least two consecutive determinations of PR (or better) at least 4 weeks or one determination of PR where confirmation not required prior to PD and not classified as PR. SD: one determination of SD (any duration) prior to PD and not classified as CR or PR. PD: one determination of PD (any duration) and not classified as CR, PR or SD. Unknown: not classified as CR, PR, SD or PD.

^b Overall response rate: Patients with best overall response rate of CR or PR.

^c Clinical benefit rate: Patients with best overall response rate of CR (any duration), PR (any duration) and SD with duration of 24 weeks or longer.

N: The total number of patients in the treatment group. It is the denominator for percentage (%) calculation.

n: Number of patients who are at the corresponding category.

CI: Confidence interval. The 95% CI for the frequency distribution of each variable were computed using the Clopper-Pearson method.

Programmer note: This table is not created by Kaplan Meier method. It is a summary of descriptive statistics based on week 20 and week 50 CRF data. n is the number of patients with non-missing data.

Table 8.1.2 Overall Response Rate *Overall and in Asian Subgroup - Per Protocol Set*

This table will be created using the same layout as Table 8.1.1.

Table 8.1.3 Time to Overall Response Overall and in Asian Subgroup – Full Analysis Set

	Asian (N=xx)		Non-Asian (N=xx)		Total (N=xxx)	
	No. of patients at Risk	Event-free probability estimates (%) ^c	No. of patients at Risk	Event-free probability estimates (%) ^c	No. of patients at Risk	Event-free probability estimates (%) ^c
Time to Overall Response ^a						
Week 4	xxx	x.x	xxx	x.x	xxx	x.x
Week 10	xxx	x.x	xxx	x.x	xxx	x.x
Week 20	xxx	x.x	xxx	x.x	xxx	x.x
Week 30	xxx	x.x	xxx	x.x	xxx	x.x
Week 40	xxx	x.x	xxx	x.x	xxx	x.x
Week 50	xxx	x.x	xxx	x.x	xxx	x.x
Etc. (as appropriate)	xxx	x.x	xxx	x.x	xxx	x.x
Total number of events, n (%)	xx (xx.x)		xx (xx.x)		xx (xx.x)	
Total number of censored, n (%)	xx (xx.x)		xx (xx.x)		xx (xx.x)	
Percentiles (95%CI) (weeks) ^b						
25 th percentile	xx.x (xx.x, xx.x)		xx.x (xx.x, xx.x)		xx.x (xx.x, xx.x)	
Median	xx.x (xx.x, xx.x)		xx.x (xx.x, xx.x)		xx.x (xx.x, xx.x)	
75 th percentile	xx.x (xx.x, xx.x)		xx.x (xx.x, xx.x)		xx.x (xx.x, xx.x)	

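### SAP Table 8.1.1 footnote a gives a best response of SD only when an SD scan exists, so a single unconfirmed PR or CR without one is tabulated as PD or Unknown

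*SAP*

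**What the plan says.** SAP section 1.2, Table 8.1.1, footnote a first defines best overall response as the best response recorded between baseline and progression. It then gives an ordered set of rules:

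- PR: "PR: at least two consecutive determinations of PR (or better) at least 4 weeks or one determination of PR where confirmation not required". The rule ends "where confirmation not required prior to PD and not classified as PR".
- SD: "SD: one determination of SD (any duration) prior to PD and not classified as CR or PR".
- PD: "PD: one determination of PD (any duration) and not classified as CR, PR or SD".
- Residual: "Unknown: not classified as CR, PR, SD or PD".

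The CR rule has the same form as the PR rule, with a confirmed and an unconfirmed branch. The footnote does not say which branch applies. The protocol does, in 10.6.1.1: "To be assigned a best overall response of PR at least two determinations of PR or better at least 4 weeks apart before progression". It sets the same requirement for CR.

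Protocol Appendix 1, section 14.1.16, agrees with the footnote's opening definition: "The best overall response is the best response recorded from the start of the treatment until disease progression/recurrence". In the supplied text that section gives best-response rules for CR and PR only.

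Table 8.1.2 (Per Protocol Set) and the four subgroup response tables (S1.8.1.1 to S4.8.1.1) reuse the Table 8.1.1 layout.

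**The concern.** A patient who shows PR at Week 10 and PD at Week 20 has a response recorded before progression. Her PR is unconfirmed, so the PR row is closed to her. The SD row is closed too, because no scan was itself read as SD. She drops into the PD row, beside patients who never had disease control. If she has no further evaluable scan after the PR, she becomes Unknown.

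This contradicts the opening sentence of the same footnote. It also orders patients oddly: SD, then PR, then PD is reported as SD, whereas PR, then PD, with the earlier shrinkage, is reported as PD.

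At stake are the SD, PD and Unknown rows, each reported with an exact 95% interval, and in some cases CBR, a key secondary endpoint. Short scan sequences are foreseeable. The study closes country by country as everolimus becomes reimbursed or commercially available, and a switch to commercial drug is a listed reason for ending treatment.

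**Working it through.** The plan states no figure to reproduce here; protocol 10.7 says the study is descriptive, without hypothesis testing.

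**Inputs.** Confirmation is required (protocol 10.6.1.1). Scans are every 10 weeks (protocol Table 7-2), so adjacent scans satisfy the 4-week gap. After a CR, only CR, unknown or PD can follow (14.1.16). A reading below 30% reduction after a single PR, without progression, is SD (14.1.16).

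**Step 1: apply the rules in order.**

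| Scans in order | Footnote as written, confirmation required | SD rule changed to SD or better | Footnote as written, unconfirmed branch used |
|---|---|---|---|
| PR, PD | PD | SD | PR |
| CR, PD | PD | SD | CR |
| PR only | Unknown | SD | PR |
| CR only | Unknown | SD | CR |
| PR, unknown, PD | PD | SD | PR |
| Unknown, PR, PD | PD | SD | PR |
| SD, PR, PD | SD | SD | PR |
| PR, SD, PD | SD | SD | PR |
| SD, CR, PD | SD | SD | CR |
| PR, CR, PD | PR | PR | CR |

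In columns two and three the PR exclusion is read as CR, its evident meaning.

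**Step 2: how general is it?** All sequences of up to three scans were listed. These are possible patterns, not patient frequencies.

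- All scans evaluable: 16 patterns contain a CR or PR that the footnote leaves unconfirmed. Of these, 12 are SD, 2 are PD and 2 are Unknown. The four that fail are the first four rows of the table.
- Unknown scans allowed: 42 patterns, of which 21 are SD, 6 PD and 15 Unknown. Changing the SD rule moves all 6 + 15 = 21 to SD. Three of them (PR, unknown, PR; PR, unknown, CR; CR, unknown, CR) fail confirmation only because the SAP demands consecutive determinations, which protocol 10.6.1.1 does not. That is a separate matter.
- In no pattern does the SD repair change whether the patient counts towards ORR.

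**Step 3: CBR.** The SAP counts SD towards CBR when it lasts at least 24 weeks, and Table 8.2.1 times SD from treatment start. With PR at the first scan and PD at the next scheduled one, PD falls no later than Week 20 + 2 = 22, below 24. CBR is lost only if an unknown or missed scan lies in the sequence and progression-free time reaches 24 weeks, as in PR, unknown, PD at Week 30, or unknown, PR, PD at Week 30.

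**Step 4: size.** The documents give no proportion of patients with a lone first response. As an illustration only:

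- Final median PFS in the cited phase III trial is 7.82 months, about 34.0 weeks. Under an exponential model, 1 − exp(−ln 2 × 10/34.0) = 0.184 progress per 10-week interval.
- Assume 5–10% of patients have a PR at the first scan, and 10–20% of those have no later scan.
- Low: 0.05 × (0.184 + 0.10) = 1.4%. High: 0.10 × (0.184 + 0.20) = 3.8%.
- Rounded outward to 1–4%: 0.01 × 198 ≈ 2 and 0.04 × 400 = 16. Here 198 is enrolment at 30 June 2014 (Amendment 2 rationale) and 400 is the planned maximum (10.7).

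For scale, suppose the PD row held 80 of 400 (20.0%, exact 95% interval 16.2–24.3%) and 8 of those patients belonged in SD. The row would become 72 of 400 (18.0%, 14.4–22.1%).

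**The case against.** **The footnote may not be the only rule.** The appendix list of best-response rules stops after PR, and its last item looks incomplete. Rules for SD, PD and unknown may have been lost in reading the PDF, or may sit in a separate analysis plan. That stands as a caution against saying that no SD rule exists elsewhere. It does not rescue the footnote, which is itself the derivation attached to the table and conflicts with its own opening sentence.

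**The two branches cannot both bite.** If the unconfirmed branch is used, a single PR is PR and nobody falls to PD or Unknown. That is correct, but the table would then report an unconfirmed ORR, which 10.6.1.1 does not allow. Section 14.1.16 calls confirmation optional in some trials, so a programmer could plausibly choose either branch.

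**Stronger readings a reader might infer, which the documents do not support:**

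- *Every unconfirmed responder is reported as PD or Unknown.* Any SD scan before progression keeps her in SD, and PR followed by CR is PR.
- *The words "where confirmation not required prior to PD and not classified as PR" cause the result.* They do not. They are an evident slip for CR; read literally, they are circular and do not keep confirmed CRs out of PR. The PD or Unknown result comes from the missing allowance for scans better than SD.
- *CBR is broadly understated.* The loss is narrow. Even in PR, unknown, PD at Week 30, the last adequate assessment before PD is Week 10, so 24 weeks of control is thinly documented.
- *The number affected can be computed from the median PFS.* That applies the all-patient hazard to responders, whereas 14.1.22 describes good-risk responders as tending to stay in response.

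**Conclusion.** The point holds in a limited form. With confirmation required, footnote a sends a patient with a single unconfirmed PR or CR and no SD scan to PD or Unknown, against its own definition of best response. PD and Unknown are overstated and SD is understated, in the main table and in those that copy it. ORR does not move when the SD rule is repaired, PFS is not involved, and CBR is touched only in the circumstances of step 3. The PR exclusion slip and the leftover unconfirmed branch are separate wording errors in the same place.

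The count of 2–16 patients rests wholly on the assumed 1–4% and should be read as a scale, not an estimate. Severity is moderate: these are descriptive tables for secondary endpoints in a study whose primary endpoint is safety, but the rule gives a wrong category and should be corrected before programming.

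**What to change.** Reword footnote a to Table 8.1.1:

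- State that confirmation is required, as in protocol 10.6.1.1.
- SD: at least one scan of SD or better before PD, including an unconfirmed CR or PR, in a patient who does not qualify for CR or PR.
- PD: progression with no earlier CR, PR or SD.
- PR: change the exclusion so that it removes patients already classed as CR.
- Delete the unconfirmed branch here and in the footnotes to Tables 8.1.3 and 8.2.1.

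The change carries over to Table 8.1.2 and the four subgroup response tables. The cost is footnote edits and one derivation; no new data are needed.
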